13.4.6.1. Supplementary Analyses

Analysis for key secondary endpoint will be repeated on PPS.

13.4.7. Exploratory Efficacy Endpoints

The exploratory efficacy endpoints are provided in Section 5.

Exploratory efficacy endpoints will be summarized by treatment group and visit using descriptive statistics. Cochran-Mantel-Haenszel chi-square tests will be used to compare treatment groups with respect to the proportion-based binary efficacy endpoints and a mixed model repeated measures or analysis of covariance will be used to compare treatment groups with respect to continuous efficacy endpoints. Negative binomial models will be used for any exploratory analyses of exacerbation rates, and stratified log-rank test will be used for any time-to-event driven exploratory analyses. Analyses will be conducted based on observed data using the FAS.

13.4.8. Safety Analysis

The safety endpoints are provided in Section 5.

The analyses of safety will be based on the SS.

Safety data will be summarized using frequency tables (counts with percentages) and will be presented by treatment and scheduled time, if appropriate. Continuous safety data will be summarized using descriptive statistics by treatment and scheduled visits and timepoints, if applicable.

Summaries will be provided by scheduled visit and time point. Data collected at unscheduled times will be listed but will not be included in summaries by scheduled visit.

Safety endpoints to be summarized include AEs, injection site reactions, vital signs (BP, pulse, respiratory rate, and temperature), ECG parameters, and safety laboratory data (hematology, clinical chemistry, and urinalysis).

13.4.8.1. Adverse Events

AEs will be coded using the Medical Dictionary for Regulatory Activities. TEAEs are defined as any AEs that occur or worsen during the Treatment Assessment Period, whether or not considered related to the treatment. The incidence of TEAEs will be presented overall, by system organ class, and by preferred term (PT) for each treatment group. Incidence of TEAEs by severity and relationship to IP will also be presented for each treatment group. Deaths, SAEs, AESIs and AEs resulting in discontinuation from the IP or trial will be summarized by treatment group.

In addition, AEs occurring during the Follow-up Period will be summarized for participants followed during that period.

A listing will be provided for all participants who experience a TEAE, SAE, discontinue IP or trial prematurely because of AEs, and temporarily interrupt IP because of AEs. AESIs will also be listed.

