4.2.2. Clinical Experience

Rademikibart has been evaluated in 3 Phase 1 studies in healthy adults, one Phase 1b trial in participants with atopic dermatitis [AD]), and 5 Phase 2 studies (3 in participants with AD, 1 in participants with asthma, and 1 in participants with nasal polyps). Phase 1 studies demonstrated that rademikibart is safe and well-tolerated, with no treatment-related serious adverse events (SAEs) and only mild-to-moderate treatment-emergent adverse events (TEAEs).

In Phase 2 studies, rademikibart showed potential as an effective and safe treatment for AD, asthma, and nasal polyps. It significantly improved disease severity and symptom control, with a

safety profile comparable to placebo. Most TEAEs were mild-to-moderate, and no SAEs related to rademikibart were reported.

In a single-ascending dose trial involving 40 healthy adult participants, single SC doses of rademikibart (75 mg, 150 mg, 300 mg, 600 mg) or placebo were administered, with an additional cohort administered a 30-minute intravenous infusion of 300 mg rademikibart or placebo. Rademikibart exposure following SC dosing increased in a greater-than-dose-proportional manner, indicating a nonlinear component to clearance. The absolute bioavailability was 58%, and the median time to the last detectable drug concentration ranged from 14 days at 75 mg to 56 days at 600 mg. Single SC doses significantly reduced serum TARC levels, a biomarker in AD and other inflammatory conditions. As shown in this trial, a single 600 mg SC dose results in substantially higher rademikibart exposure up to 28 days relative to the other SC dose levels, with all dose levels similarly well tolerated.

A comparative bioavailability trial conducted in healthy adults, comparing SC dosing of rademikibart 300 mg administered from a pre-filled syringe (PFS) relative to the same dose administration from a vial, indicated pharmacokinetic (PK) similarity of the 2 product presentations.

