6.3. Treatment Assignment

Participants will be randomized in a 1:1 ratio to 1 of the following double-blinded treatment groups, stratified by severity of the acute COPD exacerbation (requiring hospitalization or not [yes/no]) at baseline, and baseline smoking status [current or former]:

- **Rademikibart** 600 mg dose administered as 4 SC injections of 1 mL (150 mg) each.
- **Matching Placebo** administered as 4 SC injections of 1 mL each.

IP (rademikibart 600 mg SC or placebo SC) will be administered on Day 0 as per the SoA (Table 5).

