6.4. Participant Duration

For participants who consent to participate in the trial while in a stable condition, the duration of the trial will be up to 34 weeks, which includes a Screening Period of up to 26 weeks, a 28-day Treatment Assessment Period, and a 28-day Follow-up Period.

For participants who consent to participate in the trial during the urgent healthcare visit for an acute COPD exacerbation, the duration of the trial will be approximately 8 weeks, which includes a Screening Period of up to 48 hours, a 28-day Treatment Assessment Period, and a 28-day Follow-up Period. A participant is considered to have completed the trial if they have completed all periods of the trial including the Follow-up Visit (Week 8). The end of the trial is defined as the date of the last visit of the last participant in the trial globally.

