11.3.4. Suspected Drug-induced Liver Injury

DILI refers to a liver injury induced by various chemical drugs, biological products, herbal medicines and their metabolites or even excipients. Hy's Law can facilitate assessment of severe liver injury predominated by hepatocellular injury. It specifically refers to cases that meet all of the following 3 criteria:

For participants with normal liver function tests at baseline:

1. ALT or AST $\geq 3 \times$ ULN during Treatment Assessment Period, and
2. Total bilirubin $> 2 \times$ ULN during Treatment Assessment Period; without cholestasis at baseline (serum alkaline phosphatase [ALP] increased), and
3. No other identifiable causes explaining the simultaneous elevation of aminotransferases and total bilirubin, such as viral hepatitis A, B, C or E or other acute liver diseases, or concomitant use of other drugs that may induce liver injury.

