19. APPENDICES

APPENDIX A. SCHEDULE OF ASSESSMENTS

The SoA for participants who complete the planned treatment is presented in [Table 5](#).

Table 5: Schedule of Assessments

Procedures	Screening		Randomization/ Baseline/ Administration	IP Treatment Assessment						Follow-up
	V1a ^a	V1b ^{a,b}		V2 ^c	V3 ^d	V4 ^d	V5	V6	V7 ^e	
DAY	Up to 26 weeks to D-1	Up to 48 hours to D0	0	1	2	3	7 ±2 days	14 ±2 days	28 ±3 days	56 ±3 days (EOT)
WEEK							1	2	4	8
Written informed consent and HIPAA	X	X ^a								
Demographics	X	X ^a								
Previous medical and surgical history ^f	X	X ^a								
Chest X-ray or CT		X								
Verify eligibility criteria	X	X								
Smoking status review	X	X					X		X	X
Prior & concomitant medications	X	X	X	X	X	X	X	X	X	X
e-diary registration & training			X ^g							
Review e-diary						X	X		X	X
Interventional Treatment /Rescue Medication										
Randomization and assignment of trial product kit number			X							
IP administration			X							
Review rescue medication use			X	X	X	X	X		X	X

Procedures	Screening		Randomization/ Baseline/ Administration	IP Treatment Assessment						Follow-up
	V1a ^a	V1b ^{a,b}		V2 ^c	V3 ^d	V4 ^d	V5	V6	V7 ^e	
DAY	Up to 26 weeks to D-1	Up to 48 hours to D0	0	1	2	3	7 ±2 days	14 ±2 days	28 ±3 days	56 ±3 days (EOT)
WEEK							1	2	4	8
Safety										
Complete physical examination ^h	X	X								X
Symptom-directed physical examination ^h			X	X	X	X	X		X	
Assess injection site(s) ⁱ			X	X	X	X	X		X	
Body weight, height ^j	X	X							X	X
Vital signs, oxygen saturation ^k	X	X	X	X	X	X	X		X	X
ECG (12 lead) ^l	X	X					X			X
Hematology, clinical chemistry, urinalysis ^m	X	X ⁿ	X ⁿ				X		X	X
Pregnancy (β-hCG blood) test ^o	X	X								
Urine pregnancy test ^p			X						X	X
AE reporting, including SAEs and AESIs	X	X	X	X	X	X	X	X	X	X

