APPENDIX K. DRUG-INDUCED LIVER INJURY

Drug-induced liver injury (DILI) refers to a liver injury induced by various chemical drugs, biological products, herbal medicines and their metabolites or even excipients.

1. Criteria for fulfillment of Hy's Law

Hy's Law can facilitate assessment of severe liver injury predominated by hepatocellular injury. It specifically refers to cases that meet all of the following 3 criteria:

For participants with normal liver function tests at baseline:

1. Alanine aminotransferase (ALT) or aspartate aminotransferase (AST) $\geq 3 \times$ ULN during treatment period;
2. Total bilirubin $> 2 \times$ ULN during treatment period; without cholestasis at baseline (serum alkaline phosphatase [ALP] increased);
3. No other identifiable causes explaining the simultaneous elevation of aminotransferases and total bilirubin, such as viral hepatitis A, B, C or E or other acute liver diseases, or concomitant use of other drugs that may induce liver injury.

2. Retest and confirmation

For participants with normal liver biochemistry parameters at baseline, if ALT or AST $> 3 \times$ ULN is detected, the liver-related biochemistry parameters should be retested within 48 to 72 hours whenever possible to confirm and assess the trend of changes. When ALT or AST is significantly elevated above $3 \times$ ULN (eg, ALT or AST increased to $> 5 \times$ ULN) or total bilirubin is significantly elevated above $2 \times$ ULN, immediate retest of the liver biochemistry parameters is recommended.

For participants with abnormal liver biochemistry parameters at baseline, a comprehensive evaluation should be made taking into account the above criteria, with reference to the following criteria as recommended:

1. ALT or AST $\geq 3 \times$ baseline value during treatment period;
2. An increase in total bilirubin by $1 \times$ ULN during treatment period; without cholestasis at baseline (serum ALP increased);
3. No other identifiable causes explaining the simultaneous elevation of aminotransferases and total bilirubin, such as viral hepatitis A, B, C or E or other acute liver diseases, or concomitant use of other drugs that may induce liver injury.

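### The treatment-emergent AE window closes at Day 28 of an 8-week post-dose trial, so no specified table gives 8-week incidence of all AEs; the two statements of the Hy's Law window also need reconciling

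*Protocol*

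**What the plan says.** **Treatment-emergent AEs.** Section 13.4.8.1: "TEAEs are defined as any AEs that occur or worsen during the Treatment Assessment Period". Incidence by system organ class and preferred term, and by severity and relationship to IP, is specified for TEAEs. For later events the same section adds only that "AEs occurring during the Follow-up Period will be summarized for participants followed during that period". The summary of deaths, SAEs, AESIs and AEs leading to discontinuation is stated without any period limit.

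**Periods and dosing.** Section 6.4 gives "a 28-day Treatment Assessment Period, and a 28-day Follow-up Period". Section 6.3: "IP (rademikibart 600 mg SC or placebo SC) will be administered on Day 0". There is no later dose.

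**Drug persistence.** Section 4.2.2, on the single-ascending-dose trial in healthy adults: "the median time to the last detectable drug concentration ranged from 14 days at 75 mg to 56 days at 600 mg".

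**Data collection.** Section 11.6 records AEs up to the last visit, or to 28 days after dosing if that is later. In the Schedule of Assessments (Appendix A), the row "Hematology, clinical chemistry, urinalysis" is marked post-dose at Weeks 1, 4 and 8.

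**Hy's Law.** Section 11.3.4 places both laboratory criteria in the named 28-day period; the bilirubin criterion reads "ULN during Treatment Assessment Period; without cholestasis at baseline". Appendix K gives the same criterion as "ULN during treatment period; without cholestasis at baseline", a term the protocol does not define. Section 11.7.3 ties the 24-hour DILI report to cases suspected of meeting Hy's Law.

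**The concern.** Day 28 is the horizon of the primary efficacy endpoint. It does not mark a change in treatment, because the only dose is given on Day 0 and by the protocol's own data the drug is typically still detectable after that day. Elsewhere the protocol uses eight weeks as its post-dose horizon: contraception through Day 56 (Section 7.1), blood donation (Section 7.3.4), pregnancy notification (Section 11.7.5) and AE recording (Section 11.6). The TEAE definition does not follow.

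What is at stake is how the safety profile is read. An ordinary non-serious AE that starts in Week 6 is collected but is absent from the tables by SOC, PT, severity and relationship, which are the tables most readers use. Section 13.4.8.1 also names a set of listings, and a non-serious Follow-up event that is not an AESI and leads to no discontinuation is in none of them.

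The liver passages raise a separate question. One section and one appendix define the same case over differently worded periods, and the last scheduled liver panel falls after the shorter of the two.

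**Working it through.** **1. The plan's own duration.** Section 6.4: 28 + 28 = 56 days = 8 weeks. This reproduces the stated duration of approximately 8 weeks for participants who consent at the urgent visit (screening there adds at most 48 hours).

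**2. Share of time outside the TEAE window.** Inputs: window 28 days (Section 6.4); median time to last detectable concentration 56 days (Section 4.2.2).
- (56 − 28) / 56 = 50%.
- If the period is taken to end at the Week 4 visit, scheduled at Day 28 ± 3: (56 − 31) / 56 = 45% to (56 − 25) / 56 = 55%.

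**3. Why two period summaries do not give 8-week incidence.** Let *a* participants have an event in Days 0–28 and *b* in Days 29–56. The number with at least one event over 8 weeks lies anywhere from max(*a*, *b*) to *a* + *b*, depending on overlap. Neither summary shows the overlap. The second also has a different denominator, because it covers only participants followed in that period.

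**4. What this could do to a displayed incidence (assumption, not a document figure).** Take a true 8-week risk *r*.
- If every first onset falls by Day 28, the TEAE table shows *r* and nothing is lost.
- If the hazard is constant over 56 days, it shows 1 − (1 − *r*)^(28/56). For *r* = 10%: 1 − √0.90 = 5.1%. For *r* = 5%: 1 − √0.95 = 2.5%.

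Across these two shapes, a 10% risk appears as anything from 5.1% to 10%. The documents do not say which shape applies, and it will differ by event type.

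**5. The liver passages side by side.**

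| Place | Period for the ALT/AST and bilirubin criteria |
|---|---|
| Section 11.3.4 | Treatment Assessment Period (28 days) |
| Appendix K | 'treatment period', undefined for a single dose |
| Appendix A | Post-dose chemistry at Weeks 1, 4 and 8 |

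Read literally, Section 11.3.4 cannot use one of the three scheduled post-dose panels. The boundary also matters at Week 4. Appendix K asks for a retest within 48 to 72 hours, so an ALT rise found on Day 28 would be retested on Day 30 or 31. A bilirubin value that first qualifies on that retest would then fall after the period in Section 11.3.4. Appendix K does not settle which reading is meant.

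**The case against.** **The definition is a disclosed choice and loses no data.** It applies equally to both arms, AEs are recorded to Week 8, and Follow-up events are summarised. That all stands: the gap is one of definition and presentation, not of collection.

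**Section 13 is a summary and the SAP holds the detail.** Table 2 sets the endpoint as incidence of AEs, not of TEAEs, and nothing bars an all-trial table in the SAP, which is not shown. This is fair as to table layout. But the TEAE window is fixed in the protocol itself, so a SAP that follows it inherits the 28-day cut.

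**Stronger readings that a reader might infer, and that the text does not support:**
- *That all main safety definitions stop at Day 28, so AESI or SAE incidence is understated.* The AE, SAE and AESI definitions carry no such limit, and neither does the sentence on summarising deaths, SAEs and AESIs.
- *That participants with events in both periods are wrongly counted twice.* Appearing in two period-specific tables is normal, and the protocol nowhere adds them.
- *That half the drug exposure is ignored.* The 56 days is a median time to last detectable concentration in healthy adults, with non-linear clearance. It says nothing about the share of AUC or of effect after Day 28.
- *That a late liver signal goes unhandled.* The Appendix K retest trigger has no day limit. Section 11.2.6 requires clinically significant abnormal results during participation to be repeated, Section 11.3.1 makes them AEs, and an event meeting SAE criteria is reported within 24 hours under Section 11.7.1. What is unclear is only whether such a case meets the DILI definition.

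**Conclusion.** The point holds in a limited form. As written, the specified SOC, PT, severity and relationship tables omit AEs with onset in Days 29 to 56, and no specified table gives cumulative incidence of all AEs over the 8 weeks. By time, 50% of the post-dose follow-up and of the median detectable period is outside the window (45% to 55% if the period ends at the Week 4 visit). The effect on a displayed incidence cannot be fixed from the documents: it is nil if all onsets are early and close to a halving under an assumed constant hazard. Deaths, SAEs and AESIs are not affected.

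The Hy's Law point is an inconsistency. Section 11.3.4 and Appendix K word the period differently, and neither is aligned with the Week 8 laboratory draw. The documents do not show which window the sponsor intends.

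**What to change.** 1. **Section 13.4.8.1:** define TEAEs as AEs with onset or worsening from IP administration through the Week 8/EOT visit, and produce the SOC, PT, severity and relationship tables on that basis. Keep Day 0–28 and Day 29–56 as secondary cuts.
2. **Sections 13.4.8.2, 13.4.8.3 and 13.4.8.5:** align the concomitant-medication period and the treatment-emergent label for vital signs and ECG with the revised window.
3. **Section 11.3.4 and Appendix K:** reconcile the two statements of the Hy's Law period with each other and with the laboratory schedule. The text should make clear whether a qualifying elevation first seen in the Follow-up Period meets the definition that triggers the 24-hour report in Section 11.7.3. Which window applies is for the sponsor to decide.

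The cost is wording: the AE and Week 8 laboratory data are already collected. The small downside is that stated TEAE incidences will be higher in both arms than under the 28-day definition; the Day 0–28 cut keeps that figure available.

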13.4.8.2. Concomitant Medications

Medication names will be coded according to the World Health Organization Drug Dictionary. Prior and concomitant medications will be summarized overall and by drug classification and preferred name by treatment group.

Prior medications summaries will be restricted to medications stopped before the date of first IP dose. The summary of concomitant medications will comprise all medications taken during the Treatment Assessment Period, including medications ongoing at entry.

13.4.8.3. Vital Signs

The change in vital signs (BP, pulse, respiratory rate, body temperature) from baseline to each visit will be summarized by visit and treatment group descriptively including mean, standard deviation, minimum, 25th percentile, median (50th percentile), 75th percentile, and maximum values. The number and percentage of participants with a treatment-emergent potentially clinically significant values will be summarized.

13.4.8.4. Laboratory Values

The change in each of the laboratory parameters from Baseline to each visit will be summarized by visit and treatment group descriptively including mean, standard deviation, minimum, 25th percentile, median (50th percentile), 75th percentile, and maximum values.

Laboratory parameters will be classified as ‘low’, ‘normal’, or ‘high’, depending on whether the value is below, within, or above the reference range, respectively. Shift tables based on the low/normal/high categories may be produced showing the categories at Baseline against those at each visit. Listings with laboratory parameters outside the reference range flagged will be provided.

13.4.8.5. ECG Data

Ventricular rate, RR interval, QT interval, QTcF, PR interval, and QRS duration values at each timepoint, and CFB at each timepoint after first dose will be summarized. The number and percentage of participants with a treatment-emergent potentially clinically significant ECG value will be summarized (for ECG, Visit 1b serves as the baseline). A listing of participants with extreme values or changes will be provided.

13.4.9. Anti-drug Antibodies

ADA status (positive vs negative) at each visit will be summarized by treatment group. If considered relevant, descriptive statistics including number of participants, mean, standard deviation, median, and range of the actual ADA titers by treatment group and visit will be provided. The ADA status across the trial for each participant (positive vs negative) will also be classified and summarized by treatment group.

The association of ADA status across the trial (positive vs negative) with AEs/SAEs may be evaluated. In addition, the association of ADA titers (\geq median titer in positive participants vs $<$ median titer) with AE/SAEs may be evaluated for ADA-positive treated participants only. The ADA-positive participants across the trial may also be divided into persistent positive vs transient positive. A participant will be considered as persistent positive if he/she has positive ADA for ≥ 2 consecutive visits with ADA assessment. Otherwise, the participant will be considered as transient ADA-positive. The associations between ADA and AE/SAEs may be summarized for both persistent positive participants vs transient positives participants.

Evaluations of nAb will be conducted on those serum samples that test positive for ADA. The test sample is deemed positive or negative for the presence of nAb to rademikibart relative to a predetermined (in assay validation), statistically derived cut point.

All participants with titer information will be listed.

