
experiencing an acute COPD exacerbation.
	
 • Rate of moderate and severe COPD exacerbations (subsequent to the index exacerbation) over the 8-week period compared to placebo. • Acute exacerbation rate (all subsequent COPD exacerbations) over the 8-week period compared to placebo.

 • To evaluate the incidence of immunogenicity (anti-rademikibart antibodies: ADAs and nAbs) in participants with COPD and an eosinophilic phenotype experiencing an acute COPD exacerbation. 	
 • Incidence and duration of treatment-emergent ADAs and nAbs.

 • To evaluate the PK of rademikibart in participants with COPD and an eosinophilic phenotype experiencing an acute COPD exacerbation. 	
 • PK concentrations and, if calculable, PK parameters of rademikibart.

 • To evaluate the pharmacodynamics of rademikibart in participants with COPD and an eosinophilic phenotype experiencing an acute COPD exacerbation. 	
 • CFB in FeNO. • CFB in biomarkers in the blood (including but not limited to peripheral blood eosinophil count, eotaxin-3, CRP, total immunoglobulin E, TARC, and PARC).

 • To evaluate the effect of rademikibart compared with placebo as an adjunct to standard therapy on lung function in participants with COPD and an eosinophilic phenotype experiencing an acute COPD exacerbation. 	
 • Change from the earliest available measurements in pre-BD FEV₁ (absolute and percent changes, percentage predicted) at Week 1, Week 4, and Week 8. • CFB in post-BD FEV₁ at Day 1 and Day 2, and during the Follow-up Period at Week 8. • CFB or the earliest available measurements in other lung function measurements: pre-BD and post-BD FVC and FEV₁/FVC at scheduled timepoints.

 • To evaluate the effect of rademikibart compared with placebo as an adjunct to standard therapy on healthcare resource 	
 • Length of stay in an urgent healthcare facility, ED, or hospital (hours).

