- For participants who consent to participate in the trial during the urgent healthcare visit for an acute COPD exacerbation, Visit 1b should be completed immediately after providing written informed consent and verifying eligibility.

b The Screening Period after Screening Visit 1b is up to 48 hours. Any procedures completed as part of the assessment and treatment of the COPD exacerbation may be used for Screening (eg, hematology, clinical chemistry, urinalysis, β -hCG if applicable, spirometry, chest X-ray or CT, ECG). Note that the maximum combined number of chest X-rays and/or CT scans must not exceed 2 for screening.

c Randomization/Baseline Visit is defined as Day 0 (Visit 2). Screening Visit 1b and Day 0 (Visit 2) may be the same day or up to 48 hours apart. If Visit 1b and Day 0 (Visit 2) are the same day, then FeNO and post-BD spirometry do not need to be repeated. For ECG, complete physical exam, and height/weight the Visit 1b assessment will serve as Baseline. All assessments at Visit 2 (Day 0) are to be conducted pre-IP dose administration with the exception of the assessment of SC injection sites and post-IP administration vital sign measurements.

d Visit 3 and Visit 4 are for participants who are hospitalized for current acute COPD exacerbation. Hospitalized participants discharged from the hospital prior to Visit 3 or Visit 4, or participants that were not hospitalized, should return to the trial site or have a home health care visit for spirometry assessments at Visit 3 and Visit 4 when feasible.

e At Visit 7, participants will be contacted by telephone.

f Medical history includes COPD history, COPD exacerbation history, past and current medical conditions (including cardiovascular and cerebrovascular medical history, surgical history), and substance usage.

g Participants will be trained on home use of the e-diary at Visit 2 and throughout the trial on an as needed basis. Participants will complete the assessment of EXACT-PRO every evening, and Dyspnea NRS and usage of short-acting rescue medications via e-diary twice daily at home.

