- n* Screening Visit 1b: Due to the short screening window, local laboratory results will be used for the purpose of determining the participant's eligibility for randomization. Local laboratory samples should be taken at Screening Visit 1b and the results should be received and reviewed prior to randomization to allow review of the applicable eligibility criteria. If local laboratory results from the assessment of the current COPD exacerbation are already available within 72 hours prior to Screening Visit 1b, these results can be used for determination of participant's eligibility. For all randomized participants, a sample for central laboratory analysis should be obtained before IP administration on Day 0 as baseline.
- o* For women of childbearing potential, must be negative prior to IP administration. Analyzed at a local laboratory.
- p* For women of childbearing potential, analyzed at a local laboratory. Visit 2 collection is only required if Screening and the Baseline Visit (Day 0) are not on the same day.
- q* On Day 0, PK and ADA/nAb samples will be collected prior to administration of IP. On days when PK and ADA/nAb sample collection are coinciding, the samples can be taken at the same time.
- r* Venous blood gas will only be assessed in hospitalized participants.
- s* Spirometry assessments include FEV₁, and FVC (both the absolute measurement, and the percentage of predicted normal value will be recorded. Spirometry will be performed preferably in the morning; afternoon is allowable in the exceptional circumstance when morning spirometry cannot be performed. If the participant can tolerate BD washout, at Visit 6, Visit 8, Visit 9, and on the day of discharge (only for hospitalized participants), pre-BD spirometry will be performed prior to administering maintenance COPD medication(s). Participants should withhold their usual maintenance therapies on the day(s) when pre-BD spirometry is being performed as below: Withholding the last dose of salbutamol/albuterol or levosalbutamol/levalbuterol for at least 6 hours; withholding the last dose of LABA for at least 12 hours (ultra-long

- acting LABA like vilanterol should be withheld for at least 24 hours); withholding the last dose of ipratropium bromide for at least 8 hours; withholding the last dose of LAMA for at least 24 hours. This washout period will be verified before performing the measurements.

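### The persistent/transient ADA rule calls a first positive at the last sample transient, and lets the pre-dose Day 0 sample count towards persistent

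*Protocol*

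**What the plan says.** The exploratory immunogenicity endpoint in Protocol Section 5 (Table 2) is "Incidence and duration of treatment-emergent ADAs and nAbs", and the immunogenicity paragraph of the synopsis plans to summarise it by treatment group.

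Section 13.4.9 describes the analysis. It states that "The ADA status across the trial for each participant (positive vs negative) will also be classified and summarized by treatment group". It then adds an optional split: "The ADA-positive participants across the trial may also be divided into persistent positive vs transient positive". Persistent requires positive results at two or more "consecutive visits with ADA assessment". All remaining positives fall under one catch-all: "Otherwise, the participant will be considered as transient ADA-positive". The section says that associations with AEs and SAEs may be summarised for the two classes. It neither uses nor defines the term treatment-emergent.

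On sampling, a footnote to the Schedule of Assessments (Appendix A) says: "On Day 0, PK and ADA/nAb samples will be collected prior to administration of IP". Section 13.3 requires that pre-dose sample, and as few as one evaluable post-dose sample, for the immunogenicity population. Section 12.3 asks for a final-visit serum sample from withdrawn participants. Planned follow-up ends at Week 8 (Day 56).

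**The concern.** Transient is a statement about resolution: the antibody was there and then was not. The catch-all reaches that label without asking for a negative result after the positive one. A participant who is first positive at the last sample is therefore reported as having had a transient response when nothing is known about what followed.

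The rule also counts visits without saying that they must be post-dose. Day 0 is a visit with an ADA sample, so reactivity that existed before any drug was given can supply one of the two positives needed for persistent. The endpoint is about antibodies that emerge on treatment, so the class and the endpoint describe different things.

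What is at stake is the description of the antibody response in the study report and, if it is run, the persistent-versus-transient comparison of AEs and SAEs. The primary and secondary efficacy results are not involved.

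**Working it through.** The plan states no ADA figure to reproduce. The check is to apply the rule as worded to every possible sequence of results.

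**Inputs.** Persistent = at least one pair of adjacent positive ADA visits; otherwise, if any sample is positive, transient (Section 13.4.9). Day 0 counts as an ADA visit (Appendix A). The ADA row of the Schedule of Assessments is not readable in the text at hand, so four post-dose schedules were assumed, from very sparse to dense.

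**Example: assumed samples at Days 0, 28 and 56.** There are 2³ − 1 = 7 sequences with at least one positive.

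| Day 0 | Day 28 | Day 56 | Class as written | What the data show |
|---|---|---|---|---|
| − | + | − | transient | emerged, later negative |
| − | + | + | persistent | emerged, still positive |
| − | − | + | transient | emerged, nothing known afterwards |
| + | − | − | transient | pre-existing only |
| + | + | − | persistent | pre-existing, later negative |
| + | − | + | transient | pre-existing, intermittent |
| + | + | + | persistent | pre-existing, throughout |

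The third row is the first error. The fifth row is the clearest form of the second: a participant who was positive before dosing and negative by the end is called persistent. In the seventh row the label also describes reactivity that was there before dosing.

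**Does it depend on the schedule?** The same enumeration on all four assumed schedules:

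| ADA days assumed | Sequences with a positive | Last-sample-only positive is classed | Persistent only because Day 0 counts |
|---|---|---|---|
| 0, 56 | 3 | transient | 1 |
| 0, 28, 56 | 7 | transient | 1 |
| 0, 7, 28, 56 | 15 | transient | 2 |
| 0, 1, 2, 3, 7, 28, 56 | 127 | transient | 8 |

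Both errors appear on each schedule. The reason is structural: a single positive can never form an adjacent pair, and Day 0 plus the first post-dose sample always can. For a participant with only one post-dose sample, whom Section 13.3 admits, every treatment-emergent positive must be called transient and persistent can be reached only through Day 0.

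These are counts of possible sequences, not expected numbers of participants.

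**The case against.** The strongest reply is that little hangs on this. The endpoint is exploratory, and the split and the AE/SAE associations are all things that may be done. No hypothesis test or sample size depends on them. Section 13.4.9 also summarises ADA status at each visit and lists all participants with titer information, so a reader could reclassify anyone. TEAEs are confined to the 28-day Treatment Assessment Period, with Follow-up AEs summarised separately, so a first positive after Day 28 comes after the TEAE window. The positive-versus-negative contrast does not use the split; only a participant positive solely at Day 0 could affect it. All of this stands and limits the severity. It does not make the labels right, and the rule is stated in the protocol rather than left to the SAP.

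A second reply is that the operational definition of treatment-emergent is ordinary SAP content. That also stands, and its absence is not the point here. The point is that the counting rule, as fixed, admits a pre-dose visit.

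Two stronger readings are tempting, and the documents do not support them.

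- A reader might infer that ADA duration cannot be measured. It can be bounded. The lower bound is last positive day minus first positive day; the upper bound is next negative day minus previous negative day. With samples at Days 0, 28 and 56, positive at Day 28 only gives 0 to 56 − 0 = 56 days, and positive at Days 28 and 56 gives at least 56 − 28 = 28 days. With a Day 7 sample added, positive from Day 7 to Day 56 gives at least 56 − 7 = 49 days. Reporting with censoring is normal practice, and the derivation is commonly left to the SAP.
- A reader might infer that a large share of lasting responses will be mislabelled, because "At Visit 7, participants will be contacted by telephone" (Day 14) and because, after single SC doses in healthy adults, "the median time to the last detectable drug concentration ranged from 14 days at 75 mg to 56 days at 600 mg". Neither statement gives ADA onset times or incidence. Any percentage would rest on an assumed onset distribution and on an ADA schedule that cannot be seen here.

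**Conclusion.** The rule in Section 13.4.9 is wrong as written in two respects: it calls last-sample-only positives transient without an observed negative, and it lets a pre-dose positive count towards persistent although the endpoint is treatment-emergent ADA. This conclusion rests on the plain wording of the section and on Day 0 being an ADA visit. It does not depend on the unseen part of the sampling schedule.

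The severity is minor. The effect is confined to an exploratory endpoint and an optional classification, and no participant count can be derived from the documents. No conclusion is drawn that duration is unmeasurable or about the proportion misclassified.

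**What to change.** Amend Section 13.4.9, before unblinding, as follows:

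- Apply the persistent/transient rule only to treatment-emergent positives, and count post-dose samples only.
- Report participants positive at Day 0 separately as pre-existing. Whether a rise in titer over a positive Day 0 sample also counts as emergent can be set in the SAP.
- Call a participant transient only if a later sample is negative.
- Class those positive only at the last available sample as *indeterminate (last sample positive)*, whether that sample is Day 56 or the final visit after withdrawal.
- State where an intermittent sequence belongs (positive, then negative, then positive at the last sample), so that the classes are exhaustive.

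No new samples or visits are needed. The cost is one more category in the tables and fewer participants in the transient class, which makes the optional AE/SAE comparison for that class thinner.
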